# 7. GENERAL ISSUES FOR STATISTICAL ANALYSIS

# 7.1 Adjustment for Covariates

Cox proportional hazard models will have vaccine group as the main effect. For the primary objectives age, prior COVID-19 vaccination in the preceding 3 years and week will be adjusted for (time-varying covariate). Prior COVID-19 vaccination will be categorized (1 prior vaccine (2 course vaccination), 2 prior vaccines (initial vaccination and 1 booster), 3 prior vaccines and  $\geq$ 4 prior vaccines), if there are less than 30 people in a category, then we will collapse down (e.g.  $\geq$ 3 instead of 3 and  $\geq$ 4) until we have stable estimates.

Other baseline characteristics will be included as covariates if there are significant imbalances between vaccine groups and kept in the model if they adjust the hazard ratio by  $\geq 5\%$ . If there is evidence that the proportional hazard assumption is not met, weekly SARS-CoV-2 circulation will be added as a covariate or will be investigated for stratifying the baseline hazard. Covariates will not be used in subgroup models, where they are the event of interest. Season will not be included in models of SARS-CoV-2 type and subtype if they only occur in one season. If an analysis has <10 events, an unadjusted model only will be calculated.

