6.1.2 VE Primary Objective

The primary analysis for VE will be a superiority test comparing vaccine efficacy (VE) between participants who receive either the NVX 2023-2024 updated vaccine (Arm 1) or Pfizer mRNA 2023-2024 updated vaccine(Arm 2) with the non-vaccinated participants who are recommended to be vaccinated based on CDC, state or organizational guidelines but decline the 2023-2024 updated vaccine. Cox proportional hazards models will use the Andersen and Gill counting method⁴² with participants able to contribute time at risk for each day of follow-up. Cox proportional hazard models will have randomized vaccine group versus the non-randomized arm as the main effect. For both primary objectives age, prior COVID-19 vaccination in the past 4 years and week will be adjusted for (time-varying covariate). Prior COVID-19 vaccination will be categorized (Never vaccinated, 1 prior vaccine (2 course vaccination), 2 prior vaccines (initial vaccination and 1 additional vaccine dose), 3 prior vaccines and ≥4 prior vaccines), if there are less than 30 people in a category, then we will collapse down (e.g. ≥3 instead of 3 and ≥4) until we have stable estimates. Other baseline characteristics will be included as covariates if there are significant imbalances between vaccine groups and kept in the model if they adjust the hazard ratio by ≥5. If an analysis has <10 events, an unadjusted model only will be calculated.

If models for a single month do not meet the proportional hazard assumption, the Andersen and Gill counting method will be used to allow for weekly circulation as a covariate. If a model still does not meet the assumption the proportional hazards assumption after the inclusion of weekly circulation as a covariate, the Prentice, Williams, and Peterson total time model⁴³ will be used with season as a strata

and circulation as a covariate, allowing for circulation to vary. Participants who do not experience an SARS-CoV-2 case prior to the discontinuation of the study will be right censored at their last response to weekly surveillance contacts.

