# 3. RANDOMIZATION AND BLINDING

# 3.1 Method of Group Assignment and Randomization

Randomization to vaccine type for the group of participants who elect to receive a booster vaccine will be stratified by age group (18-49 years and 50+ years) and sex. If participants do not report a sex, they will be stratified in the male category. Randomization will be done after completing the Pre-vaccination Questionnaire (Appendix K) that confirms that the participant is able to receive study vaccine on the same day. Participants will be randomized within each age and sex stratum in a 1:1 treatment ratio to receive either NVX or mRNA. The stratified randomization list will be generated before enrollment starts using a computerized random-number generator to select randomly permuted group blocks of size 6 with 3 of each vaccine type in each block. The next available sequential randomization slot number within the

appropriate stratified age and sex group will be assigned to each enrolled participant at the time of randomization.

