#### 8.3. Efficacy Analysis

# **8.3.1** Primary Objective Analysis

The primary analysis for VE will be a superiority test comparing vaccine efficacy (VE) between participants who receive either the NVX 2023-2024 updated vaccine (Arm 1) or Pfizer mRNA 2023-2024 updated vaccine (Arm 2) with the participants who are recommended to be vaccinated based on CDC, state or organizational guidelines but decline the 2023-2024 updated vaccine. Cox proportional hazards models will use the Andersen and Gill counting method with participants able to contribute time at risk for each day of follow-up. Vaccine efficacy is defined as 100% × (1–HR) calculated using the Cox proportional hazards regression with vaccine group as a main effect, adjusting for age group.

$$h(t) = h_0(t) \exp(\beta V + b_i Z_i)$$

where t is the time at risk,  $\beta$  is the effect of vaccine group of interest (different for VE and rVE objectives) and  $b_i$  is the effect of covariates indicated by  $Z_i$ . The HR for VE or rVE is then defined as  $exp(\beta)$ .

For the VE objective, Cox proportional hazard models will have randomized vaccine group versus the non-randomized arm as the main effect. For both primary objectives age, prior COVID-19 vaccination in the past 4 years and week will be adjusted for (time-varying covariate). Prior COVID-19 vaccination will be categorized (1 prior vaccine (2 course vaccination), 2 prior vaccines (initial vaccination and 1 booster), 3 prior vaccines and  $\geq$ 4 prior vaccines), if there are less than 30 people in a category, then we will collapse down (e.g.  $\geq$ 3 instead of 3 and  $\geq$ 4) until we have stable estimates. Other baseline characteristics will be included as covariates if there are significant imbalances between vaccine groups and kept in the model if they adjust the hazard ratio by  $\geq$ 5. If an analysis has <10 events, an unadjusted model only will be calculated.

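### Sex stratifies the randomisation but is not a pre-specified covariate in either primary Cox model: negligible for rVE, and for VE left to a two-step data-driven rule that can discard it

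*SAP*

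**What the plan says.** SAP 3.1 states that randomisation to vaccine type "will be stratified by age group (18-49 years and 50+ years) and sex". The list is drawn up to "select randomly permuted group blocks of size 6 with 3 of each vaccine type in each block". Participants who do not report a sex are placed in the male stratum. Protocol 5.5.3 says the same.

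SAP 7.1 gives the covariates: "For the primary objectives age, prior COVID-19 vaccination in the preceding 3 years and week will be adjusted for (time-varying covariate"). SAP 8.3.1 repeats the list with a different look-back window, which is a separate matter: "For both primary objectives age, prior COVID-19 vaccination in the past 4 years and week will be adjusted for (time-varying covariate"). Protocol 6.1.2 matches SAP 8.3.1 on these three covariates. Where SAP 8.3.1 defines VE, the model is fitted "with vaccine group as a main effect, adjusting for age group". None of these places names sex, and none stratifies the baseline hazard by it.

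Anything else passes two steps. First: "Other baseline characteristics will be included as covariates if there are significant imbalances between vaccine groups". Second, it is "kept in the model if they adjust the hazard ratio by" at least 5% (SAP 7.1). SAP 8.3.1 and protocol 6.1.2 give this threshold as 5 with no unit.

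The two primary contrasts differ in kind. For VE, "Cox proportional hazard models will have randomized vaccine group versus the non-randomized arm as the main effect". For rVE the contrast is NVX against Pfizer, which is randomised 1:1.

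**The concern.** The usual principle is to analyse as randomised: a factor that restricts the allocation belongs in the model. Here one of the two stratification factors, age, is carried into the analysis and the other is not, with no reason given.

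The screening rule does not repair this, and it fails differently in the two models. In the rVE model, the stratification itself keeps sex from ever looking imbalanced. In the VE model nothing balances sex except recruitment goals, and a variable that passes the imbalance step can still be discarded for moving the estimate too little. VE is an observational contrast and is the objective that sets the sample size. A known, measured difference between the groups should be adjusted for by prior commitment, not according to what the data show.

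**Working it through.** **Inputs from the documents.** 600 enrolled per vaccine arm and 300 decliners; 15% attrition, so 510 evaluable per vaccine arm; Pfizer-arm rate 60 per 100,000 person-days over 168 days; non-inferiority margin rVE -50%, that is HR 1.5; one-sided alpha 0.05; blocks of 6 within four age-by-sex strata. The documents give no sex hazard ratio and no expected sex split among decliners beyond the recruitment goals, so those values below are assumptions.

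**1. The plan's own figure.** Non-inferiority power at rVE 10 (HR 0.9):

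- Pfizer event probability = 60 × 168 / 100,000 = 0.1008.
- NVX event probability = 1 − (1 − 0.1008)^0.9 = 0.0912.
- Events = 510 × (0.1008 + 0.0912) = 97.9.
- Power = Φ(√(97.9 × 0.25) × (ln 1.5 − ln 0.9) − 1.645) = Φ(4.948 × 0.5108 − 1.645) = Φ(0.883) = 81.13%.

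The plan states 81.12%, so the figure is reproduced.

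**2. rVE: can the imbalance rule admit sex?** A block of 3 and 3 lets a stratum end at most 3 apart. Each sex spans two strata, so it can differ by at most 6: 303 against 297 women, and the reverse for men. Chi-square = 1200 × (303² − 297²)² / 600⁴ = 0.12, p = 0.73. Before mITT exclusions, sex cannot trigger the rule.

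**3. rVE: does the omission matter?** Cox models were simulated with 4,000 trials per scenario, 1,020 evaluable participants, and vaccine balanced within the four strata. Each pair is without / with sex in the model.

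| Assumed sex HR | Power at true HR 0.9 | False non-inferiority at true HR 1.5 | Mean log-HR at 0.9 | Mean log-HR at 1.5 |
|---|---|---|---|---|
| 1.0 | 79.6 / 79.6% | 4.9 / 4.9% | −0.1060 / −0.1061 | 0.4065 / 0.4067 |
| 1.5 | 79.4 / 79.3% | 5.5 / 5.6% | −0.1072 / −0.1074 | 0.4039 / 0.4051 |
| 2.0 | 78.2 / 78.3% | 4.6 / 4.6% | −0.1042 / −0.1048 | 0.4008 / 0.4036 |

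The largest shift is 0.4036 − 0.4008 = 0.0028, about 0.3% on the hazard ratio. The mean standard error is the same to four decimals with and without sex in every row.

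**4. VE: can the imbalance rule admit sex?** Against 600 women and 600 men among the vaccinated, 169 women among 300 decliners (56.3%) gives p = 0.0497. So the rule can be triggered. At an assumed 60% versus 50% female, the pooled proportion is (180 + 600)/1500 = 0.52. The standard error is √(0.52 × 0.48 × (1/300 + 1/1200)) = 0.0323, so z = 0.10/0.0323 = 3.1 and p is about 0.002. Sex enters.

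**5. VE: does it stay?** With sex hazard ratio h (women against men), leaving sex out multiplies the vaccine hazard ratio by approximately (1 + 0.5(h − 1)) / (1 + 0.6(h − 1)).

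- h = 1.25: 1.125/1.150 = 0.978, a shift of 2.2%.
- h = 1.5: 1.25/1.30 = 0.962, a shift of 3.8%.

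Both are under 5%, so sex is dropped again. Retention needs a factor of 0.95: 1 + 0.5x = 0.95 + 0.57x, so x = 0.05/0.07 = 0.71, a sex hazard ratio of about 1.71 or more.

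On the VE scale, at a true hazard ratio of 0.5, these factors give 0.489 and 0.481. The reported VE would be 51.1% or 51.9% instead of 50%.

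**The case against.** Four points can fairly be made for the plan.

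- **The shift is below the plan's own tolerance.** SAP 7.1 treats a movement under 5% as ignorable, and 2-4% is under it. That is true, and it is why the point is minor. But the threshold decides whether an optional covariate earns its place. It gives no reason to leave out a factor the design already treats as important, and its unit is missing in two of the three places where it appears.
- **The 60% scenario departs from the recruitment goals.** Protocol Table 1 aims for at least 75 in each of four age-by-sex cells of 300, an even split if met; 60% female leaves 120 men against a goal of 150. Protocol 5.4 presents stratified recruitment as a help to comparability, and protocol 8.4 monitors participation by sex. This stands: if the goals are met closely, sex does not confound VE. However, the table is titled an illustration, and protocol 5.4.1 sets out an effort to reach the minimums, not a guarantee.
- **The rVE text leaves some room.** SAP 8.3.1 and protocol 6.1.3 refer to adjustment for potential confounders or baseline differences. That permits sex but does not pre-specify it.
- **The effect on rVE cannot be demonstrated.** This stands in full.

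A reader might infer that stratification bars sex from both primary models. The documents do not support this: the decliners are outside the randomisation, and an imbalance of the size considered here would be caught at the first step. A reader might also infer that the rVE test has a materially wrong variance or a diluted hazard ratio. The simulations show neither over the sex hazard ratios assumed.

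**Conclusion.** The point holds, and it is minor. Sex is a stratification factor and is missing from the pre-specified covariates of both primary models.

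For rVE, the imbalance rule has no practical route to add it. The consequence is a departure from analysing as randomised, with no material effect on power, error rate or estimate for sex hazard ratios from 1.0 to 2.0. For VE, the weakness is the retention step: a statistically significant sex imbalance can be found and then left unadjusted. The cost there is 2-4% on the vaccine hazard ratio, if 60% of decliners and 50% of vaccinees are women and the sex hazard ratio is 1.25 to 1.5. Those values are assumptions, and the direction of any real imbalance is unknown. Neither primary sample size nor any stated power figure needs revision.

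**What to change.** In SAP 7.1, SAP 8.3.1 and protocol 6.1.2, name sex beside age group as a fixed covariate in both primary Cox models, and exempt it from the imbalance and 5% rules. Define it as recorded for stratification, with unreported sex in the male category, and apply the same coding to the decliners. For the rVE model, stratifying the baseline hazard by the four randomisation strata is an acceptable alternative. Use the same model in the per-protocol analysis.

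While editing, settle whether the age term is age or age group, and restore the percent sign to the threshold in SAP 8.3.1 and protocol 6.1.2.

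The cost is one line in each of three places. Sex is already collected and is needed to randomise, so there is no new data collection and no change to the sample size.

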5.1 Overview of Study Design

Approximately 1,500 adults 18 years and older from Salt Lake City, UT and surrounding areas (60-mile radius) will be enrolled in a randomized trial to be followed until Summer 2024. This trial will employ a stratified recruitment approach to ensure there is sufficient variability in sex and age within the cohort. For those that are in the intervention group, their randomization occurs at their vaccination appointment. Information on socio-demographics, employment information, occupational responsibilities, exposure to SARS-CoV-2 virus, history of SARS-CoV-2 infection, COVID-19 and flu vaccine history, health status and conditions, PPE use, pre-vaccination intention, and knowledge and attitudes about SARS-CoV-2 infection control practices will be collected by self-report through an enrollment survey. Information on previous COVID-19 vaccination history and concomitant medications will be collected at enrollment by study staff.

[figure not shown]
Following participant enrollment, active surveillance will be conducted weekly to identify acute illness symptoms via secure short message service (SMS) text messages. Participants will also be asked to proactively notify study staff if they develop symptoms during the week. To determine acute illness, participants will be asked if they developed subjective COVID-like illness (CLI) symptoms since the day of their last scheduled surveillance. CLI symptoms include fever, chills, malaise, fatigue, headache, cough, shortness of breath, sore throat, runny nose or nasal congestion, nausea or vomiting, diarrhea, muscle or body aches, and change in smell/taste. Each week, regardless of symptoms, participants will self-test with an at-home COVID-19 rapid antigen test (RAT) and upload a photo of the results to the database platform. When an acute illness and/or a positive COVID-19 test is identified, participants will self-test with an at-home COVID-19 antigen test on day 0, day 1, and test again on day 3. When illnesses are identified, participants will describe their symptoms, illness severity, duration, impact on functioning through resolution of their illness, and report any treatments/interventions and medical visits for SARS-CoV-2 infection.

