5.2 Study Population

Study Population: Individuals aged 18 years and older who: 1) reside in Salt Lake City, Utah and surrounding areas and 2) have previously received at least 2-doses of mRNA COVID-19 vaccine before joining the trial. Those from the greater Salt Lake City community partners, including participants from previously established cohorts who have consented to be contacted for future studies, will be invited to participate in the trial. The use of existing cohorts of college and graduate students, healthcare personnel (HCP), first responders (FR), and other essential workers (EW) has several advantages:

- We will only contact individuals from previous studies who gave permission to re-contact them about future studies. These studies include: the 2020-2023 "Research on the Epidemiology of SARS-CoV-2 in Essential Response Personnel (RECOVER)" study; the 2021-2022 "Pediatric Research Observing Trends and Exposures in COVID-19 Timelines (PROTECT)" study; and the 2022-2023 "Randomized Participant- and Investigator-Blinded Trial to Compare the Clinical Efficacy of Recombinant Influenza Vaccine to Standard Dose Egg-Based Inactivated Influenza Vaccine among Adults Aged 18-64 Years in the United States (RAIVEN)" study. Given their existing relationship with the research team, we anticipate these participants will be more likely to agree to participate.
- Enrollment of many participants within the same work facility and/or community facilitates estimation of incidence among individuals with similar exposures.
- Recruitment from closed systems such as healthcare facilities opens the opportunity to
 calculate participation rates and examine potential participation biases related to age,
 gender, occupation, location, or other basic socio-demographic information.
- Vaccination status for some participants can be documented via a review of existing study records or other vaccine registries.

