# 7.4 Subgroups

Subgroup analysis will be performed with the subgroup as a categorical variable and tested for interaction with vaccination.

The efficacy analyses will be performed for the following subgroups as feasible:

Time since last immune challenge (prior vaccine or infection) as a category of >1 year, 6 months-1 year, 3 to 6 months and age category (18-49 and 50+)

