# **Efficacy**

#### Time at Risk

- Beginning of time at risk starts with the first active surveillance contact
- End of time at risk is illness onset with rapid test confirmed SARS-Co-v2 virus infection or the last submitted response to study surveillance.
  - o Illness onset is defined for participants with an illness as the earlier of the first positive swab collection (excluding false positives) and the date of reported symptom start.
- Duration of time at risk in days is defined as: End of time at risk beginning of time at risk + 1.
- We will assess the need to statistically adjust for time since last infection or time since last vaccination as 2 separate potential covariates

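### For the self-selected vaccinated-versus-decliner comparison, most measured confounders reach the primary Cox model only through a screen that can drop several modest imbalances at once

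*SAP*

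**What the plan says.** Protocol 5.5.3 (Blinding) has participants elect or decline vaccination, so the comparator of objective 1 is self-selected.

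**Always in the model.** SAP 7.1: "For the primary objectives age, prior COVID-19 vaccination in the preceding 3 years and week will be adjusted for". SAP 8.3.1 and Protocol 6.1.2 name the same three terms with a four-year look-back. SAP 8.3.1 also defines VE as "calculated using the Cox proportional hazards regression with vaccine group as a main effect, adjusting for age group".

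**Conditional.** SAP 7.1: "Other baseline characteristics will be included as covariates if there are significant imbalances between vaccine groups and kept in the model" if the hazard ratio changes by at least 5%. Protocol 6.1.2 says "kept in the model if they adjust the hazard ratio by ≥5" without a unit, and SAP 8.3.1 does the same. No candidate list, significance level for the imbalance test or order of entry is given.

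**Left open.** SAP 7.5 (Time at Risk): "We will assess the need to statistically adjust for time since last infection or time since last vaccination as 2 separate potential covariates". SAP 7.4 plans a subgroup analysis by "Time since last immune challenge (prior vaccine or infection) as a category of >1 year, 6 months-1 year, 3 to 6 months", but that does not adjust the primary estimate.

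**Collected at enrolment.** Protocol 5.1 lists "history of SARS-CoV-2 infection, COVID-19 and flu vaccine history, health status and conditions, PPE use" and employment. Protocol 5.5.1.1 adds household composition, socio-economic status and smoking, among others.

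**Sensitivity analyses.** SAP 8.3.3 repeats the analysis in the per-protocol population and in participants above a surveillance-completion threshold. Neither varies the covariate set.

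**The concern.** Because objective 1 is not randomised, its estimate depends on the adjustment set. A significance screen asks whether an imbalance is detectable in this sample, and the retention step asks whether that one variable moves the hazard ratio by 5%. Neither asks whether several variables together matter. Four imbalances that each move the hazard ratio by 2 or 3% can all fail the rule while their joint effect exceeds 5%.

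The planning rates show why this could count. Protocol 6.1.1 expects 48 against 60 cases per 100,000 person-days, which implies VE = 1 − 48/60 = 20%. SAP 4.1 expects 68 against 80, which implies 1 − 68/80 = 15%. At that level a shift of 5 to 7 points is a sizeable part of the effect. The open wording in SAP 7.5 also lets two analysts reach different primary estimates from the same data.

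**Working it through.** **1. The plan's own figure.** Inputs from Protocol 6.1.1: decliner event probability 0.1008 over 24 weeks (hazard 0.10625), 4:1 allocation, VE 56.25% (HR 0.4375), two-sided alpha 0.05, 80% power, 15% attrition. Schoenfeld events = (1.960 + 0.842)² / (0.8 × 0.2 × ln(0.4375)²) = 71.8. Vaccinated event probability = 1 − (1 − 0.1008)^0.4375 = 0.0454, so the mean is 0.2 × 0.1008 + 0.8 × 0.0454 = 0.0565. N = 71.8 / 0.0565 / 0.85 ≈ 1,496, against the stated 1,500. The sample size reproduces and is not in dispute.

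**2. One factor under the rule.** The documents give no confounder prevalences or effects, so everything from here on is assumed. Take a binary factor that multiplies the hazard by h, with prevalence 25% in the vaccinated and 30% in decliners. Omitting it multiplies the hazard ratio by about (1 + 0.25(h − 1)) / (1 + 0.30(h − 1)).

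| h | one factor | four factors | VE if all four are omitted, true VE 20% |
|---|---|---|---|
| 0.5 | 0.875/0.850 = 1.029 | 1.123 | 1 − 0.8 × 1.123 = 10.2% |
| 0.6 | 0.900/0.880 = 1.023 | 1.094 | 12.5% |
| 0.7 | 0.925/0.910 = 1.016 | 1.068 | 14.6% |

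Each factor alone falls below 5%; the four together exceed it. At 25% against 40% with h = 0.5 the single-factor shift is 0.875/0.800 = 1.094, which passes.

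**3. The whole rule, simulated.** Cox models, 1,200 vaccinated and 300 decliners, 15% dropout, age and four-level prior doses always fitted. A factor is kept if the two-proportion p is below 0.05 and the hazard ratio changes by at least 5%.
- One factor, h = 0.5: at 25% vs 30% it is flagged in 40% of trials and kept in 14%. At 25% vs 40% it is kept in 90%.
- Four independent factors, each 25% vs 30%, true VE 20%, h = 0.5 / 0.6 / 0.7: none is kept in 55% / 74% / 87% of trials. Median VE is 12.8% / 13.4% / 14.8% under the plan, against 19.6% / 19.7% / 19.7% with one prespecified score term. A separate repeat gave 12.6% (h = 0.5) and 15.5% (h = 0.7), against 19.0% and 19.8%.
- Imbalance reversed, h = 0.5: 25.9% against 19.6%.
- Two factors in each direction: 19.5% under the plan and 18.9% with the score, so no shift to correct.
- Half of the imbalance explained by prior doses: 15.3% against 19.8%.
- True VE 56.25%: 52.4% against 56.1%, or 59.6% against 56.0% with the imbalance reversed.
- True VE 0, in a simpler constant-hazard simulation with four risk-raising factors commoner in decliners: 30% vs 25% gives 5.0% (h = 1.5) and 6.4% (h = 2) under the rule, against −1.6% and −1.4% fully adjusted. 30% vs 20% gives 4.9% and 2.8%, against −1.4% and −1.1%.

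**4. Size relative to noise.** In the first four-factor case the shift in log hazard ratio is ln(0.872/0.804) = 0.081, against a standard error of 0.223. Coverage is 92 to 95% throughout the Cox cases. With true VE 0 and the imbalance favouring the vaccinated, VE > 0 is falsely claimed in 7.0% (h = 0.5) or 4.3% (h = 0.7) of trials under the plan, against 3.4% or 2.6% with the score. The nominal rate in that direction is 2.5%.

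**The case against.** **Adjustment is not absent.** Age, prior doses and week are always fitted, and Protocol 5.4 and 5.4.1 set recruitment goals by age and sex. This stands, but those goals do not balance infection history, health, occupation or behaviour.

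**The missing unit is a slip.** SAP 7.1 gives 5% for the same rule, which settles the unitless 5 elsewhere. SAP 7.5's two variables can also be read as candidates for the 7.1 rule. Both points are fair; neither fixes the set in advance.

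**The larger shifts need a particular pattern.** They require several independent factors, same direction, each too small to pass alone. Opposing imbalances cancel, and prior doses may absorb part. This stands, and it limits the weight of the point.

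**Deleting the screen would do harm.** A reader might infer that the screen should simply be replaced by a fixed list. That fails when a strong confounder is off the list. With one unlisted factor at 25% vs 40% (hazard halved, true VE 20%), the plan gives 19.7% and a score without it 12.3%. Reversed, with true VE 0, VE > 0 is falsely claimed in 2.3% of trials under the plan and 6.6% with the score alone. Keeping the screen on top of the fixed set removes this: 20.0% in the first case, and 20.2% against 12.6% under the plan when modest listed factors and a strong unlisted one are both present. The empirical SD at VE 56.25% is 0.261 with or without the addition.

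**Conclusion.** The point holds as a modest, inexpensive improvement to objective 1. The rule handles a large single imbalance well and tends to lose several modest ones in the same direction. The shift is about 4 to 8 VE points when true VE is 0 to 20% and about 3 to 4 points at 56.25%, in each case under one standard error. These sizes rest wholly on assumed prevalences and effects.

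Three stronger readings are not supported. The documents do not show that VE will be biased in favour of the vaccine, because nothing in them gives the direction of any imbalance. They do not show that the comparison is unadjusted or its test invalid: three terms are fixed, and simulated coverage stays at 92 to 95%. The randomised NVX-versus-mRNA comparison does not share the problem. There the only remark is that sex, a randomisation stratum, is not a named covariate, and the expected numerical effect of that is negligible.

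**What to change.** For objective 1, in SAP 7.1, 7.5 and 8.3.1 and Protocol 6.1.2:

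- Keep age, prior-dose category and week. Settle age versus age group and the three- versus four-year look-back in the same edit.
- Always adjust, whatever any test shows, for an enrolment-only set named in advance: sex, time since last infection, time since last vaccination, any chronic condition, occupation group and PPE use at enrolment. Consider the other collected items, such as influenza vaccine history, household composition and socio-economic status.
- The set may enter as one prespecified propensity-score term. With about 72 events (Protocol 6.1.1) and week not counted, vaccine, age, three prior-dose terms, sex and the score make 7 terms, or 72/7 = 10.3 events each. Separate entry needs about 16 terms, or 72/16 = 4.5 each.
- Retain the screen, with 5% stated consistently, as a further step for baseline variables outside the set. Exclude mask use during circulation (listed in SAP 8.2), which is measured after vaccination.
- In SAP 7.5, replace the open assessment with inclusion of both variables.
- Add sex to both primary models (minor, no real cost).

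The cost is wording plus a small power loss, which depends on how much vaccination choice the added variables explain beyond age and prior doses. If little, it is negligible: at VE 56.25% the simulated standard error was 0.244 with the score against 0.242 under the plan. If a further 10%, scaling the events by 0.9 gives Φ(√(72 × 0.9 × 0.16) × 0.827 − 1.96) = 75.9%, against 80.1% without the factor. Treat that as an upper bound: variation already explained by age and prior doses must not be charged to the change. Objective 2 gains only sex, so its power is essentially unchanged.
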